4.2.4. Change in Gonorrhea Test Result (T1 to T3)

Gonorrhea infections will be assessed at baseline and 8-month follow up using oral, anal, and urine samples. Each of the three tests yields a positive (1) or negative (0) result. Change in test result will be calculated by subtracting the baseline result from the 8-month follow-up result. Oral, anal, and urine tests will be treated as separate outcomes.

4.2.5. Reactive HIV Test (T3)

Testing for HIV will be assessed at baseline and 8-month follow up. The test yields a reactive (1) or non-reactive (0) result. The outcome for reactive HIV test will use the T3 test result.

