### 3.4 Biological Specimens

Project staff members who have completed mandatory training will conduct HIV/STI testing. Study participants will be screened for drug use and STIs such as chlamydia, gonorrhea, syphilis, and HIV

infection at the baseline and follow-up visits. Clinical specimens may include 15-20 mL first-catch urine, anal swab (GC,CT), oral/laryngeal swab, and finger stick. Participants with reactive STI or HIV tests will be referred to affiliated clinics at each site for evaluation and treatment. All participant referral clinics will be comprehensive and follow the Ryan White HIV/AIDS Programming instruction as developed by the HRSA HIV/AIDS Bureau. Senior Investigators are practicing physicians at study referral sites with experience in YMSM and YTW health, and will provide any subsequent mental health, medical case management, and psychosocial support service referrals as needed for participants. Following the protocols of our previous studies involving HIV testing, HIV-positive participants at follow-up will not receive HIV testing if they produce documentation of a previous diagnosis (e.g., medications, lab report). In addition, phase 3 participants with a known HIV positive status at the time of consent will not receive HIV testing at baseline or follow-up.

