#### 4.1.4 Phase 2 Intervention Pre Test & Pilot-Test Inclusion Criteria

Must meet the following eight criteria:

1. Male or assigned male at birth (YTW)
2. Identifies as a man who has sex with men (YMSM) and/or gay bisexual man or transgender woman/transwoman
3. Identifies as African American/Black, Hispanic/Latino, and/or as a racial/ethnic minority or person of color
4. 16-24 years old
5. English-speaking (primary)
6. HIV negative or of unknown status
7. Currently unemployed but seeking employment or employed only part-time 35 hrs or less on avg/wk)
8. Able to attend a 4-session employment program

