## 6.2 Baseline/Enrollment

After informed consent and eligibility has been confirmed, participants will undergo biological specimen collection for HIV/STIs screening and drug testing. Please note that for Phase 3, if a participant has a known positive HIV status they will not undergo HIV testing. Participants will be given an iPad tablet and headphones and asked to complete an ACASI survey. The survey includes items on: sociodemographics, employment variables, HIV risk behavior variables, and potential modifying variables including perceived transgender discrimination scale, job seeking self-efficacy, managing interview, resilience, employment and job search, integrated motivations, internal self-concept, goal internalization, perceived social support, drug use, alcohol use, sexual history, commercial sex work, homelessness, condom intentions, money inventory, and PrEP awareness.

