## **6.5 Intervention Follow-Up**

For Phase 2 the follow-up visit (T3) is scheduled for 8 months post-intervention ( $\pm 4$  weeks), and for Phase 3 the follow-up visit is scheduled for 3 months post-intervention ( $\pm 2$  weeks). At this visit, participants will repeat biological specimen collection for HIV/STIs screening and drug use. If a participant already has a known positive HIV status they will not undergo HIV testing. Participants will repeat the ACASI survey with items on sociodemographics, employment variables, HIV risk behavior variables, and potential modifying variables such as perceived transgender discrimination scale, job seeking self-efficacy, managing interview, resilience, employment and job search, integrated motivations, internal self-concept, goal internalization, perceived social support, drug use, alcohol use, sexual history, commercial sex work, homelessness, condom intentions, money inventory, and PrEP awareness.

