### 8.3 Compensation

**Focus Groups:** Participants will receive \$40 each for focus group participation.

**Key Informant Interviews:** LGBTQ-friendly employers will be offered a \$10 gift card for key informant interview participation. All other participants will receive \$40 for key informant interview participation.

**CAB:** \$30 per meeting.

**Intervention Pre-Test:** Participants will receive \$30 for completing visit surveys at T1 and T2, \$40 for providing optional biologic specimens at T1, and \$20 per workshop session attended, for a possible total of \$180.

**Intervention Pilot:** Participants will receive \$30 for completing visit surveys at each time point, \$40 for providing optional biologic specimens at T1 and T3, \$40 per workshop session attended, for a possible total of \$330.

**Intervention Community Pilot:** Participants will receive \$30 for completing visit surveys at each time point, \$40 for providing optional biologic specimens at T1 and T3, and \$30 per workshop session attended, for a possible total of \$290.

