1.1. Objectives and Research Hypotheses

The primary objective of Phase 2 is to pilot-test the intervention among up to 70 at-risk YMSM and YTW of color in order to evaluate feasibility and acceptability. Investigators hypothesize the intervention will increase job self-efficacy and readiness, as well as decrease HIV risk behaviors and STI and HIV infections.

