3.1. Intent-to-Treat Population

All participants who completed T3 will be included in intent-to-treat analyses involving variables measuring changes from T1 to T3 (see sections 4.1.3-4.1.4 and 4.2.1-4.2.5 below).

All participants who completed at least one workshop will be included in intent-to-treat analyses involving workshop evaluation and workshop completion variables (see sections 4.1.1,

¹ The original inclusion criteria included "Considered 'at-risk' for HIV based on 6-item risk assessment". The removal of this criterion was approved on August 16, 2018 as part of protocol v4.0 and eligibility was rerun retrospectively for those who completed the Screener Survey (SCR) prior to the inclusion criteria modification.

4.1.2 below). This population will form the basis for both the primary and secondary analyses of the efficacy and safety endpoints.

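### Both SAPs score HIV from the T3 test alone, so a new infection diagnosed between visits can drop out and an older infection can be counted

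*SAP*

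**What the plan says.** **HIV outcome.** Section 4.2.5 of each SAP says HIV is tested at T1 and T3, and then: "The outcome for reactive HIV test will use the T3 test result". The algorithm in Appendix 2.5 of each SAP reads only the T3 collection form. No T1 HIV variable is derived, and T1 HIV status is not among the covariates in SAP 5.5. Section 3.1 of each SAP nonetheless places 4.2.5 among "variables measuring changes from T1 to T3 (see sections 4.1.3-4.1.4 and 4.2.1-4.2.5 below", and section 1.1 hypothesises that the intervention will "decrease HIV risk behaviors and STI and HIV infections".

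**Who is tested.** Protocol 6.5 says of T3: "If a participant already has a known positive HIV status they will not undergo HIV testing". Protocol 3.4 makes this conditional: "HIV-positive participants at follow-up will not receive HIV testing if they produce documentation of a previous diagnosis". At T1 the order is: "After informed consent and eligibility has been confirmed, participants will undergo biological specimen collection for HIV/STIs screening and drug testing". Protocol 8.3 pays participants "for providing optional biologic specimens at T1 and T3". Phase 2 admits people who are "HIV negative or of unknown status" (Protocol 4.1.4), while its exclusion list (4.2.3) bars, for Phase 2 only, a known positive status at baseline. Phase 3 (4.1.5) has no HIV-status criterion.

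**STI outcomes.** Chlamydia and gonorrhea change is T3 minus T1 at each anatomical site (SAP 4.2.3, 4.2.4). Paired categorical change is tested by McNemar's test at alpha 0.10 (SAP 5.1). Protocol 3.4 and 8.4.1 refer participants with positive tests for treatment or care.

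**The concern.** If the variable is to speak to a hypothesis about new infections, it has to separate infection after T1 from infection before T1. Reading T3 alone can fail in both directions.

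- **A new infection disappears.** Someone who seroconverts and is diagnosed elsewhere before T3 is the event of interest. If the diagnosis means that no T3 test is done, no SAP rule counts it.
- **An old infection is counted.** Someone with no T1 test who is reactive at T3 receives the same code as a seroconverter.

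STI and HIV infections are one of the four named study outcomes, and the pilot is meant to lead to a large multi-site trial (Protocol 2.4). With so few HIV events likely, one misrouted participant can decide what is reported.

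The STI issue is related but secondary. The study's own T1 screening and referral can clear infections, and the net test sets those clearances against new positives.

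**Working it through.** The documents give no HIV or STI rate, so there is no planned figure to reproduce. Every rate below is an assumption.

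**1. Tracing the Appendix 2.5 algorithm (same in both SAPs)**

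| Participant | Value of `HIVREAC_T3_1` |
|---|---|
| T1 non-reactive, T3 non-reactive | 0 |
| T1 non-reactive, T3 reactive | 1 |
| T1 non-reactive, diagnosed between visits, no T3 test | none (not collected) |
| No T1 test, T3 reactive | 1 |
| T1 reactive, retested and reactive at T3 | 1 |
| Phase 3 known positive, tested at neither visit | none (not collected) |

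Rows 2, 4 and 5 share a code although only row 2 is known to be a new infection. Row 3 is a new infection with no value. SAP 5.2 has no rule for row 3. Protocol 10.4 offers complete-case analysis or multiple imputation, and neither scores a known diagnosis as an event.

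**2. Who reaches rows 3 and 5**

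- Row 3: under Protocol 6.5, known positive status is enough to omit the T3 test. Under 3.4, documentation must be produced, so an undocumented diagnosis would still be tested and counted.
- Row 5: this needs Protocol 4.2.3 (Phase 2) to mean status known before the T1 test, and 6.5 not to apply to someone found reactive at T1.

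**3. Expected new HIV infections**

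Expected number = n × annual incidence × months/12, at an assumed 1–5% per year. Phase 2 uses the target of 50 completers (SAP 2.3). Phase 3 has up to 40 participants and no retention target, so 28 (0.70 × 40, borrowing the Phase 2 rate) is the lower value.

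- Phase 2, 8 months: 50 × 0.01 × 8/12 = 0.33 to 50 × 0.05 × 8/12 = 1.67.
- Phase 2, if T1 to T3 reaches 11 months because workshops may take 12 weeks: 0.46 to 2.29.
- Phase 3, 3 months: 28 × 0.01 × 3/12 = 0.07 to 40 × 0.05 × 3/12 = 0.50.

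Lost to row 3, if 25–75% of new infections are diagnosed first and not tested at T3:

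- Phase 2 (8 months): 0.33 × 0.25 = 0.08 to 1.67 × 0.75 = 1.25.
- Phase 3: 0.07 × 0.25 = 0.02 to 0.50 × 0.75 = 0.38.

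Candidates for row 4, if 5–20% have no T1 test and 2–10% of those are undiagnosed positives:

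- Phase 2: 50 × 0.05 × 0.02 = 0.05 to 50 × 0.20 × 0.10 = 1.0.
- Phase 3: 28 × 0.05 × 0.02 = 0.03 to 40 × 0.20 × 0.10 = 0.8.

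**4. Effect of one lost case (exact Clopper-Pearson 90% intervals)**

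| Phase and n | As the SAP scores it | Incident result |
|---|---|---|
| Phase 2, 50 | 0/49 (0–5.9%) | 1/50 (0.1–9.1%) |
| Phase 3, 40 | 0/39 (0–7.4%) | 1/40 (0.1–11.3%) |
| Phase 3, 28 | 0/27 (0–10.5%) | 1/28 (0.2–15.9%) |

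For one T1-untested reactive participant the two columns swap.

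**5. STI illustration**

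Take constant incidence, site prevalence P, untreated duration D and interval t, with all T1 positives cleared. Let q = P × (1 − exp(−t/D)), the chance of being positive at T3 starting from negative. Phase 2 with n = 50, P = 0.10, D = 12, t = 8 gives q = 0.0487. Expected positive-to-negative pairs are 50 × 0.10 × 0.9513 = 4.76, and negative-to-positive pairs 50 × 0.90 × 0.0487 = 2.19. The exact two-sided McNemar test at 0.10 declares a decrease with probability 12.7%, against 5% nominal in that direction, although incidence has not changed.

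The figure moves a great deal with the assumptions:

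- With t = 11 it is 8.7%.
- With P = 0.20 it is 31.6% at 8 months and 20.6% at 11.
- With P = 0.10 and half cleared it is at most 4.9%.
- With P = 0.05 the exact test gives at most 3.6% in any scenario examined, but the uncorrected chi-square version gives up to 21.5% (n = 40). Neither SAP says which version is meant.

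**The case against.** **The variable is what its label says.** It is titled and labelled as T3 reactivity, not incidence, and it measures that correctly. This stands as far as it goes: reading it as new infection is an inference from the hypothesis and from its place among the change variables. But T3 reactivity alone cannot address that hypothesis.

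**A lost case is visibly missing.** It is meant to be coded as not collected, so it is not a silent negative, and a form not shown in the documents may record the diagnosis. Both are fair. What can be said is that the printed algorithm uses no such record.

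**T1-reactive participants.** A reader might infer that they stay in the study and are certain to be counted as new cases at T3. The documents do not support that. Protocol 4.2.3 may exclude them in Phase 2, and 6.5 may stop the retest. The route exists only on narrow readings of those sections.

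**STI test.** A reader might infer that McNemar's test is wrong here. It is not: it is valid for net change, the +1 code already marks new positives, and SAP 5.1 will show frequencies at each visit. Attribution without controls is a general limit of a single-arm study, and both SAPs acknowledge that a comparison group was given up. What remains is that neither SAP mentions treatment after the study's own referral as an explanation for a fall.

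**Small secondary outcome.** These are secondary outcomes in an unpowered pilot whose primary objective is feasibility and acceptability. That limits the remedy to a definition and a caveat. It does not remove the gap.

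**Conclusion.** The point holds for HIV in both SAPs. The stated rule can drop a true new infection and can count an infection that predates T1, and the direction of the net error cannot be known in advance. At an assumed 1–5% per year, about 0.3–1.7 infections are expected in Phase 2 and 0.07–0.5 in Phase 3, so a single case can make the difference between none and one. The expected number of misrouted cases is itself small and rests on assumed shares diagnosed early or untested. The documents do not show that any such case will occur.

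For STIs the conclusion is narrower: a net decrease cannot by itself be credited to the workshops. The percentages above are illustrations that depend on prevalence, clearance, duration, the T1-to-T3 interval and the McNemar version. They are not a forecast of a false-positive rate.

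This should be corrected in the analysis plan, and it calls for no change of design. Confidence is moderate, because the forms are not shown and every rate is assumed.

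**What to change.** In both SAPs:

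1. Derive the T1 HIV result. Define incident HIV as T1 non-reactive and either T3 reactive or a positive status first documented after the T1 test.
2. Take as denominator the T1 non-reactive participants who have a T3 test or such documentation.
3. List T1-reactive, T1-untested and Phase 3 known-positive participants separately. Report the incident count with an exact confidence interval, as descriptive only.
4. Report T3 STI positivity by site, split by T1 result, with new positives among T1 negatives as the measure of new infection. If McNemar's test is kept, name the version and state that a net decrease alone is not evidence of workshop efficacy, because T1 positives were referred for treatment.
5. Editorial: in Appendix 2.5, `HIVREAC_T3_1_1` should read `HIVREAC_T3_1`.

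In the protocol, sections 3.4, 4.2.3 and 6.5 must be reconciled on who remains in the study and who is tested at T3.

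The cost is a few derivation lines, some SAP wording and a record of when a diagnosis was first documented. The study gives up an efficacy claim based on a fall in STI positivity. With no comparison group, the HIV count stays descriptive under any coding.

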#### 4.2.3 Intervention Pilot-Test Exclusion Criteria

Must not meet any of the following:

1. Individuals identify as non-Hispanic White
2. Individuals not assigned male at birth
3. Phase 2 only: Individuals with a known HIV positive-status at baseline

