2.5. REACTIVE HIV TEST

Description: Testing for HIV is conducted at Baseline (T1) and Month 8 follow-up (T3) and indicates whether or not the test result was reactive or non-reactive. The reactive HIV testing result for T3 is recorded in item 1a of the BIC2 form.

Variable: HIVREAC_T3_1

Label: Reactive HIV Test Result at T3.

Type: Numeric; Format: 0=Non-Reactive, 1=Reactive, .U=Unknown, .N=Not Collected, .R=Refused, .=Missing

Algorithm:
If [BIC2] BIC1=1 then HIVREAC_T3_1= [BIC2] BIC1a
Else if [BIC2] BIC1=1 and [BIC2] BIC1a=. then HIVREAC_T3_1=.U
Else if [BIC2] BIC1=0 then HIVREAC_T3_1_1 = .N
Else if [BIC2] BIC1=9 and [BIC2] BIC1a=9 then HIVREAC_T3_1=.R
Else if [BIC2] BIC1=. and [BIC2] BIC1a=. then HIVREAC_T3_1=.

Statistical Analysis Plan: Work2Prevent – Phase 3

PROTOCOL:	ATN 151: Work2Prevent: Employment as HIV prevention for young men who have sex with men (YMSM) and young transgender women (YTW)
PROTOCOL DATE:	May 23, 2017 Revised August 5, 2019
PROTOCOL VERSION:	5.1
CLINICALTRIALS.GOV ID:	NCT03313310
SPONSOR:	The Eunice Kennedy Shriver National Institute of Child Health and Human Development (NICHD) with co-funding from: National Institute on Drug Abuse (NIDA), National Institute of Mental Health (NIMH), and National Institute on Minority Health and Health Disparities (NIMHD)
SAP DATE:	December 13, 2019
SAP VERSION:	2.0
SAP PREPARED BY:	ATN Coordinating Center Collaborative Studies Coordinating Center Department of Biostatistics The University of North Carolina at Chapel Hill [name] [name]
AUTHORS:	[name] [name], MS [name] [name], BS [name]

SIGNATURE PAGE

Name	Role	Signature	Date
[name]	ATN CC Co-Investigator		
[name]	Principal Investigator		
[name]	Site Investigator		

TABLE OF CONTENTS

1. INTRODUCTION	7
1.1. OBJECTIVES AND RESEARCH HYPOTHESES	7
2. STUDY METHODS.....	7
2.1. STUDY DESIGN	7
2.2. STUDY POPULATION	7
2.3. SAMPLE SIZE INFORMATION	8
3. ANALYSIS POPULATIONS.....	8
3.1. PER PROTOCOL POPULATION	ERROR! BOOKMARK NOT DEFINED.
4. STUDY ASSESSMENTS	9
4.1. PRIMARY OUTCOMES	9
4.1.1. Information Systems Success Model Score (T2)	9
4.1.2. Workshop Completion (T2).....	9
4.1.3. Change in Job-Seeking Self-Efficacy Scale Score (T1 to T3)	9
4.1.4. Change in Protean Career Attitudes Scale Score (T1 to T3)	10
4.2. SECONDARY OUTCOMES.....	10
4.2.1. Change in Self-Reported Hours Worked Per Week (T1 to T3).....	10

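### Both SAPs take HIV status from the T3 test alone, so a participant diagnosed between T1 and T3, and therefore not retested, is left out of the count of new infections

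*SAP*

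**What the plan says.** Protocol 3.3 and section 2.1 of both SAPs list HIV infections, together with STIs, among the study outcomes. Section 1.1 of both SAPs hypothesises that they will fall. The variable that serves this outcome is defined in SAP 4.2.5, in the same words for both phases: "The outcome for reactive HIV test will use the T3 test result". Appendix 2.5 of each SAP derives it as `HIVREAC_T3_1` from two items of the T3 Biospecimen Collection form: `BIC1` (whether a test was done) and `BIC1a` (the result). Neither appendix derives a T1 HIV variable.

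The protocol limits who has that test. Section 3.4 says "HIV-positive participants at follow-up will not receive HIV testing if they produce documentation of a previous diagnosis", and adds for the community pilot that "phase 3 participants with a known HIV positive status at the time of consent will not receive HIV testing at baseline or follow-up". Section 6.5 repeats the rule for the T3 visit: "If a participant already has a known positive HIV status they will not undergo HIV testing".

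When no test was done, Appendix 2.5 of both SAPs reads "Else if [BIC2] BIC1=0 then HIVREAC_T3_1_1 = .N", where .N is the missing code for a test not collected.

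**The concern.** The testing rule and the outcome definition do not fit together. A participant who was non-reactive at T1, was diagnosed elsewhere and brings proof to T3 is a new infection during follow-up. That is also the person whom the protocol excuses from the T3 test, and the SAP outcome can be positive only through that test. The person is missing because of the event being counted.

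The interval leaves room for this. In Phase 2, T3 falls 8 months (±4 weeks) after workshops that may take up to 12 weeks from baseline. In Phase 3 it falls 3 months (±2 weeks) after up to 4 weeks. With so few expected events, a single omitted case can decide whether the report says zero.

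**Working it through.** **Step 1. Who is untested at T3.** Protocol 4.2.3 excludes "Phase 2 only: Individuals with a known HIV positive-status at baseline". Unless status was undisclosed at entry, the documentation rule can therefore apply in Phase 2 only to people diagnosed at or after baseline. They are of two kinds: reactive at T1 (correctly not a new infection) and non-reactive at T1 but diagnosed later (a new infection). In Phase 3 there is a third kind, known positive at consent. The T1 result and the reason for not testing separate these groups, and the SAP derivation uses neither.

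**Step 2. The derivation, run branch by branch** (Appendix 2.5, identical in both SAPs).

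| T3 situation | `BIC1` | `BIC1a` | Value of `HIVREAC_T3_1` |
|---|---|---|---|
| Tested, non-reactive | 1 | 0 | 0 |
| Tested, reactive | 1 | 1 | 1 |
| Not tested | 0 | missing | missing (.N is written to `HIVREAC_T3_1_1`) |
| Refused | 9 | 9 | .R (missing) |
| No data | missing | missing | missing |

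That an untested known positive carries `BIC1` = 0 is inferred, because the form is not in the documents. The conclusion does not depend on it: the listed non-test codes are 0, 9 and missing, and none leads to 1. The missing-data rules in SAP 5.2 do not recover these cases.

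**Step 3. Size.** The plan gives no HIV count, rate or power to reproduce. The denominators used here are illustrations: 50 Phase 2 completers (SAP Phase 2, 2.3; 50/70 = 71.4%, in line with the stated retention of about 70%) and the Phase 3 maximum of 40 (SAP Phase 3, 2.3).

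Let N be the participants at T3, k the true new infections, and d the number of those documented and so untested. Assume that everyone was non-reactive at T1 and that all others are tested.

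- SAP rule: (k − d)/(N − d)
- Rule that counts documented diagnoses: k/N

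| N | k | d | SAP rule | Documented cases counted |
|---|---|---|---|---|
| 50 | 1 | 1 | 0/49 = 0.0% | 1/50 = 2.0% |
| 50 | 3 | 0 | 3/50 = 6.0% | 3/50 = 6.0% |
| 50 | 3 | 1 | 2/49 = 4.1% | 3/50 = 6.0% |
| 50 | 3 | 3 | 0/47 = 0.0% | 3/50 = 6.0% |
| 40 | 1 | 1 | 0/39 = 0.0% | 1/40 = 2.5% |
| 40 | 2 | 1 | 1/39 = 2.6% | 2/40 = 5.0% |

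Exact (Clopper-Pearson) 95% intervals for the single-case rows are 0.05–10.6% for 1/50 against 0–7.3% for 0/49, and 0.06–13.2% for 1/40 against 0–9.0% for 0/39. For zero events the upper limit is 1 − 0.025^(1/n): 7.3% at n = 49 and 9.0% at n = 39.

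The values of k and d are assumptions; the documents give no basis for estimating either. One case weighs more if fewer people complete T3, if fewer give specimens, or, in Phase 3, once participants known positive at consent are taken out of the 40.

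**The case against.** The strongest reply is that the outcome is what its name says. SAP 4.2.5 is titled as a reactive test at T3, whereas 4.2.1 to 4.2.4 are titled as changes, and SAP 5.5 keeps the same distinction. The hypothesis in protocol 2.4 names HIV risk behaviour and not infection. The collection form or exit survey may also record known status, so the information need not be lost. And the path is narrow: non-reactive at T1, diagnosed outside the study, present at T3, with proof. All of this stands, and it keeps the point small. It does not remove it, because this is the only variable serving a listed infection outcome that both SAPs hypothesise will fall, and no written rule uses any other source.

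Three stronger readings are tempting but not supported.

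- *The misnamed variable makes the undercount worse.* It does not. Both .N and a plain missing value are missing, so the count is the same; only the reason is lost.
- *The SAPs wrongly treat this as a change variable.* That rests on a section range in SAP 3.1 that runs through 4.2.5, in a sentence about who enters the analysis. It is more likely a loose cross-reference.
- *The T3 count is inflated by infections that predate the workshops.* This is possible only at the margin. Known positives are excluded from Phase 2 and not retested in either phase. What remains is someone reactive at T1 who is retested anyway, or someone with no T1 test, since payment is described as "for providing optional biologic specimens at T1 and T3".

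**Conclusion.** The point holds as a minor one, in both SAPs. As written, a participant non-reactive at T1 with a documented diagnosis before T3 is dropped from numerator and denominator, so the T3 figure can understate new infections. Each such case costs one event: about 2.0 percentage points with 50 in Phase 2 and 2.5 with 40 in Phase 3, under the assumptions above. The number of cases is unknown and may be zero.

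A reader might infer that the plan is set up to confirm a fall in HIV infections. The documents do not support that. The omission does lower the count, but there is no T1 HIV variable to pair with T3 and no comparison group, so the outcome as defined cannot test a decrease. Counting the missing cases would not change that; it would only make the descriptive count include the right people. The conclusion rests on the written derivation and the protocol's testing rule, without sight of the form.

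**What to change.** In section 4.2.5 and Appendix 2.5 of both SAPs:

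1. Keep the T3 reactive result and label it as a screening result.
2. Add a derived variable for new HIV infection: non-reactive at T1, and either reactive at T3 or untested at T3 because of a documented HIV diagnosis. The non-reactive T1 test already places the diagnosis after baseline, so no diagnosis date is required. This matters because protocol 3.4 accepts medications as proof, and these may not show a date.
3. Exclude from its denominator anyone known positive or reactive at T1, and list those with no T1 test as undetermined.
4. Tabulate participants untested at T3 by reason, so that a diagnosis after T1 is distinguishable from known positive status at consent and from refusal.
5. As a clerical correction, assign .N to `HIVREAC_T3_1`.

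The cost is a slightly smaller denominator, a few undetermined cases and some extra coding. The reason for not testing must be taken from the T3 record; if the form has no item for it, one would have to be added. No new test or visit is needed.
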